**SUBJECT**

An individual who participates in a clinical investigation.

**SYSTEMIC INFECTION, SEPSIS**

The presence of bacteria, other infectious organisms, or toxins created by infectious organisms in the bloodstream with spread throughout the body.

**VASCULAR INJURY REQUIRING REPAIR**

Injury to the access site, and/or target vessel arterial or venous vessel wall resulting in persistent bleeding and requiring repair (via surgery, angioplasty, ultrasound-guided compression, thrombin injection, or other means).

**VASOSPASM**

The sudden, but transitory constriction of a blood vessel, potentially causing discomfort and limitation of distal blood flow.

**VASOVAGAL RESPONSE**

Development of inappropriate cardiac slowing and arteriolar dilatation.

**WOUND DEHISCENCE**

Wound rupture along a surgical incision

**WOUND SITE PAIN**

Pain at the location of incision for the endovascular procedure.

PTA	Percutaneous Transluminal Angioplasty
PRO	Patient-reported Outcomes
QVA	Quantitative Vascular Angiography
SAE	Serious Adverse Event
SADE	Serious Adverse Device Effect
SAP	Statistical Analysis Plan
SD	Standard Deviation
SFA	Superficial Femoral Artery
SOC	System Organ Class
SSR	Sample Size Re-estimation
TLF	Tables, Listings, and Figures
TLR	Target Lesion Revascularization
TVR	Target Vessel Revascularization
UADE	Unanticipated Adverse Device Effect
UCL	Upper confidence limit
YCRG	Yale Clinical Research Group

STATISTICAL ANALYSIS PLAN

1 PROTOCOL SYNOPSIS

Principal Investigator	[name] Prisma Health Midlands [name], [name] [name] University Hospitals Cleveland Medical Center, [name] [name]
Sponsor	LimFlow, Inc. [name] [name] [contact] [contact] Email: [contact]
Independent Review Committee, Clinical Events Committee, Data Monitoring Committee, Wound Core Lab, Statistical Analysis	Syntactx [name] [name] [name] [contact] [contact]
Unblinded Statistician	[name], Paradigm Statistics
Blinded Statistician	[name], Independent Contractor
Study Title	Percutaneous Deep Vein Arterialization for the Treatment of Late-Stage Chronic Limb-Threatening Ischemia (The PROMISE II Trial)
Investigational Device	LimFlow System™
Indication for Use	The LimFlow System is indicated to treat chronic limb-threatening ischemia by creating an arteriovenous (AV) connection in the below-the-knee vasculature for treatment of chronic limb-threatening ischemia (CLTI).
Intended Use	The LimFlow System is intended for endovascular, minimally invasive procedures in patients with a clinical diagnosis of chronic limb-threatening ischemia and who have been determined to have no surgical or endovascular treatment option (i.e., “no option”).
Study Objective	The objective of this US pivotal trial is to investigate the safety and effectiveness of The LimFlow System for creating an AV connection in

STATISTICAL ANALYSIS PLAN

the Below The Knee (BTK) vascular system using an endovascular, minimally invasive approach to arterialize the pedal veins to treat Chronic Limb Threatening Ischemia (CLTI) in subjects ineligible for conventional endovascular or surgical limb salvage procedures.

Study Population

The study population is comprised of subjects who are confirmed as “no option” (ineligible for conventional endovascular or surgical limb salvage procedures) by the Independent Review Committee (IRC). “No option” is defined as either a) absence of a usable pedal artery target (endovascular or surgical approach), or b) the presence of a pedal artery target with absence of a viable single-segment vein in either lower extremity or either arm that could be used for autogenous vein conduit.

Study Design

A prospective, single-arm, multi-center pivotal study designed to confirm the safety and effectiveness of The LimFlow System. The study will consist of a minimum of 60 and up to 105 subjects. This study utilizes a Bayesian Goldilocks adaptive design for sample size determination.

Number of Sites

Up to 25 sites in the United States, United Kingdom, and Japan

Primary Endpoint

Amputation Free Survival (AFS) defined as freedom from major amputation or death at 6 months, compared to a literature-based performance goal.

Major Amputation: above-ankle amputation of the index limb or

Death: all-cause mortality

Secondary Endpoints

Primary Patency: Defined as the absence of occlusion of the endovascular intervention maintained with no additional or secondary surgical or endovascular procedures, at 30 days and 6 months.

Primary Assisted Patency: Defined as the absence of occlusion of the endovascular intervention maintained with the use of additional or secondary surgical or endovascular procedures, as long as occlusion of the primary treated site has not occurred, at 30 days and 6 months.

Secondary Patency: Defined as the absence of occlusion of the endovascular intervention that is maintained with the use of additional or secondary surgical or endovascular procedures after occlusion occurs, at 30 days and 6 months.

Limb Salvage: Defined as the percentage of subjects with freedom from above-ankle amputation of the index limb, evaluated at 30 days, 3 and 6 months.

Change in Rutherford Classification: Defined as a change of one

STATISTICAL ANALYSIS PLAN

class or greater, as evaluated at 30 days, 3 and 6 months.

Technical Success: Defined as the successful creation of an arteriovenous fistula in the desired limb location with immediate morphological success.

Procedural Success: Defined as the combination of technical success, and absence of all-cause death, above-ankle amputation or clinically driven major re-intervention¹ of the stent-graft at 30 days.

Target Wound Healing: Defined as complete healing of the patient's target wound as evaluated at 30 days, 3, 6, 9 months, and 1 year.

All Wound Healing: Defined as complete healing of the patient's wounds as evaluated at 30 days, 3, 6, 9 months, and 1 year.

All Wound Area Reduction: Defined as reduction in area of the patient's wounds as evaluated at 30 days, 3, 6, 9 months, and 1 year.

Freedom from Contrast-Induced Nephropathy: Defined as subjects without acute (within 72 hours after intravenous contrast administration) impairment of renal function, measured as an absolute ≥ 0.5 mg/dL (44 $\mu\text{mol/L}$) increase compared to baseline SCr value.

Procedure Time: Defined as the time of the first puncture (venous or arterial) to when the last catheter is removed.

Radiation Exposure: Defined as patient radiation exposure (in milligray) during the procedure.

Contrast Volume: Defined as the total volume of contrast media (in milliliters) given during the procedure.

Inclusion Criteria

- 1) Subject must be > 21 and < 95 years of age
- 2) Clinical diagnosis of critical limb ischemia, defined as the following clinical assessments: previous angiogram or hemodynamic evidence of severely diminished arterial inflow of the index limb (e.g., $\text{ABI} \leq 0.39$, $\text{TP} / \text{TcPO}_2 < 30$ mm Hg) and:
 - a. Rutherford Classification 5, ischemic ulceration OR

¹ The creation of a new surgical bypass, the use of thrombectomy or thrombolysis (i.e., procedures done in the setting of lost primary-assisted patency), or major surgical revision such as a jump graft or an interposition graft performed for occlusion of the stent graft.

STATISTICAL ANALYSIS PLAN

- b. Rutherford Classification 6, ischemic gangrene
- 3) Subject has been assessed by the Principal Investigator, reviewed by the Independent Review Committee (IRC), and determined that no conventional distal bypass, surgical or endovascular therapy for limb salvage is feasible due to either a) absence of a usable pedal artery target (endovascular or surgical approach), or b) the presence of a pedal artery target with absence of a viable single-segment vein in either lower extremity or either arm that could be used for autogenous vein conduit.
- 4) Proximally, the Target In-flow Artery at the cross-over point must fall within the recommended vessel diameter ranges for the LimFlow stent graft by visual estimation.
- 5) Prior stent(s) to the infrainguinal arteries (e.g., iliac, SFA, and popliteal) are allowed.
- 6) Planned minor amputation (e.g., partial toe, ray or proximal foot/transmetatarsal) of target extremity within 30 days after the index procedure is allowed.
- 7) Subject is willing and able to sign the informed consent form.
- 8) Subject is enrolled in an acceptable wound care network and has an adequate support network to ensure that subject complies with medication regimen and follow-up study visits.
- 9) Prior to enrollment (7-day window), women of childbearing potential must have a negative pregnancy test.
- 10) The primary wound is stable (e.g., not rapidly deteriorating and/or showing signs of healing).
- 11) Stable glycemic control, HbA1C < 10% (<269mg/dL)
- 12) Subjects requiring dialysis may be included, provided they meet all these requirements:
 - a. On dialysis for > 6 months
 - b. Autologous arteriovenous (AV) fistula access used for hemodialysis
 - c. Serum albumin > 30 g/liter BMI > 20

STATISTICAL ANALYSIS PLAN

Exclusion Criteria

Subjects will be excluded from participating in this study if they meet the following criteria before initiation of the endovascular procedure:

- 1) Concomitant hepatic insufficiency, thrombophlebitis in the target limb, or non-treatable coagulation disorder within the past 90 days.
- 2) Active immunodeficiency disorder or receiving immunosuppressant therapy.
- 3) Prior peripheral arterial bypass procedure above or below the knee, which would inhibit proximal inflow to the stent graft or interventional revascularization procedure within 30 days.
- 4) Previous major amputation of the target limb or presence of a wound requiring a free flap, or absence of adequate viable tissue.
- 5) Life expectancy less than 12 months.
- 6) Documented myocardial infarction or stroke within the previous 90 days.
- 7) Active infection (e.g., fever, elevated WBC count $>20.0 \times 10^9/L$, and/or positive blood culture) at the time of the index procedure that may preclude insertion of a prosthesis or require major amputation (e.g., osteomyelitis proximal to metatarsals).
- 8) Known or suspected allergies or contraindications to aspirin or P2Y12 inhibitors, heparin, stainless steel, nitinol or contrast agent that cannot be adequately pre-treated.
- 9) Subject is taking anti-coagulants, which in the opinion of the investigator, interferes with the ability to participate in the study (i.e., intermittent interruption of therapy for a procedure may compromise subject's safety).
- 10) Lower extremity vascular disease that may inhibit the procedure and/or jeopardize wound healing (e.g., vasculitis, Buerger's disease, significant edema in the target limb, deep venous thrombus in the target vein, hyperpigmentation, or medial ulceration above the ankle).
- 11) Significant acute or chronic kidney disease with a serum creatinine of > 2.5 mg/dl in subjects not undergoing dialysis.
- 12) Severe heart failure (e.g., NYHA Class IV), which in the opinion of the investigator may compromise the ability to safely undergo a

STATISTICAL ANALYSIS PLAN

percutaneous procedure.

- 13) Any significant concurrent medical, psychological, or social condition, which may interfere with the subject's optimal participation in the study, in the opinion of the investigator.
- 14) The subject is participating in another investigational drug or device study that has not completed the primary endpoint or that clinically interferes with the endpoints of this study.
- 15) Subject is unwilling, unable, or unlikely for cognitive or social reasons to comply with the protocol or follow-up requirements.

Duration of Study

Each enrolled subject will be followed for up to 3 years (\pm 4 weeks) post-procedure. The primary endpoint assessments will be completed by 6 months (\pm 2 weeks), and secondary endpoint assessments will be completed by 12 months (\pm 1 month) post-procedure.

Follow-Up Schedule

Measures of safety and effectiveness will be assessed through hospital discharge, at 14 (\pm 3) days, 30 (\pm 7) days, at 2, 3, 6, and 9 months (\pm 2 weeks), at one year (\pm 4 weeks), two years (\pm 4 weeks), and three years (\pm 4 weeks). The study will be completed and closed after all subjects have either met a primary endpoint or completed the 3-year follow-up requirements.

Independent Review:

An Independent Review Committee (IRC), a Clinical Events Committee (CEC), a Data Monitoring Committee (DMC), and a Wound Core Lab will provide independent oversight per their respective charters.

2 SCOPE

This statistical analysis plan covers the analyses to be performed after enrolled patients reach the primary endpoint according to PROMISE II protocol (LF-CA-PR-3).

3 STATISTICAL OBJECTIVES

3.1 Primary Objective

The primary statistical objective is to determine if the test device meets its performance goal, which is to establish that the amputation free survival rate at 6 months post-index procedure is statistically higher than 0.54.

3.2 Secondary Objectives

The secondary objectives consist of determining the test device's point estimate and its precision for the following endpoints:

- **Primary Patency:** Defined as the absence of occlusion of the endovascular intervention maintained with no additional or secondary surgical or endovascular procedures, at 30 days and 6 months.
- **Primary Assisted Patency:** Defined as the absence of occlusion of the endovascular intervention maintained with using additional or secondary surgical or endovascular procedures, as long as occlusion of the primary treated site has not occurred, at 30 days and 6 months.

STATISTICAL ANALYSIS PLAN

- **Secondary Patency:** Defined as the absence of occlusion of the endovascular intervention maintained with using additional or secondary surgical or endovascular procedures after occlusion occurs, at 30 days and 6 months.
- **Limb Salvage:** Defined as the percentage of subjects with freedom from above-ankle amputation of the index limb, evaluated at 30 days, 3 and 6 months.
- **Change in Rutherford Classification:** Defined as a change of one class or greater, as evaluated at 30 days, 3 and 6 months.
- **Technical Success:** Defined as successful placement of the arterial and venous catheters in the desired location in the limb, ability to place the stent-grafts, completion of the endovascular procedure, and immediate morphological success.
- **Procedural Success:** Defined as the combination of technical success, and absence of all-cause death, above-ankle amputation or clinically driven major re-intervention of the stent-graft at 30 days.
- **Target Wound Healing:** Defined as complete healing of the patient's target wound as evaluated at 30 days, 3, 6, 9 months, and 1 year.
- **All Wound Healing:** Defined as complete healing of the patient's wounds as evaluated at 30 days, 3, 6, 9 months, and 1 year.
- **Freedom from Contrast-Induced Nephropathy:** Defined as subjects without acute (within 72 hours after intravenous contrast administration) impairment of renal function, measured as an absolute ≥ 0.5 mg/dL (44 μ mol/L) increase compared to baseline SCr value.
- **Procedure Time:** Defined as the time of the first puncture (venous or arterial) to when the last catheter is removed.
- **Radiation Exposure:** Defined as patient radiation exposure (in milligray) during the procedure.
- **Contrast Volume:** Defined as the total volume of contrast media (in milliliters) given during the procedure

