7 SECONDARY ENDPOINTS ANALYSIS

A listing of secondary endpoints is given in Section 3.2. Secondary endpoints will be evaluated with descriptive statistics, along with 95% confidence intervals computed using frequentist methods. No hypothesis tests will be conducted.

Methods:

- Secondary endpoints that are binary (e.g., technical success, freedom from contrast-induced nephropathy at 72 hours) will be summarized as a proportion, with a 95% confidence interval computed via an exact binomial calculation.

STATISTICAL ANALYSIS PLAN

- Secondary endpoints that involve the occurrence (or not) of events at times ≥ 30 days will be summarized with Kaplan-Meier time-to-event methods. Confidence intervals will be computed on the log(survival) scale.
- Continuous endpoints (e.g., procedure time, radiation exposure, contrast volume) will be summarized with means, medians, SD, quartiles, min, and max. Confidence intervals will be computed assuming approximate normality.

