Stage IV	Necrosis and/or gangrene of the limb	III	5	Minor tissue loss – nonhealing ulcer; focal gangrene with diffuse pedal ischemia	Resting AP<60mmHg, ankle or metatarsal PVR flat or barely pulsatile; TP < 40mmHg
			6	Major tissue loss – extending transmetatarsally; functional foot no longer salvageable	

Studies that only used the Fontaine classification were compared to those that only used the Rutherford classification using logistic regression. The SAS code was:

```
proc logistic data=limlos_adj;
class study status class;
freq num;
model status(event='no event')= class;
run;
```

where status is whether there was a death or major amputation event at 6 months or not, the class was the CLTI classification system used (R or F), and num is the variable that contains the number of subjects with or without an event.

The results of the logistic regression are shown in **Table 6**. The classification system effect has a low p-value (p <0.0001) and an odds ratio (Rutherford 5 or 6 versus Fontaine IV) of 2.891.

Table 6: Results of Logistic regression predicting AFS using CLTI classification method

Analysis of Maximum Likelihood Estimates						
Parameter		DF	Estimate	Standard Error	Wald Chi-Square	Pr > ChiSq
Intercept		1	0.5020	0.0766	42.9900	<.0001
class	FIV	1	0.5308	0.0766	48.0546	<.0001
Odds Ratio Estimates						
Effect		Point Estimate	95% Wald Confidence Limits			
class FIV vs R56		2.891	2.141	3.903		

The 6-month AFS rates in studies shown in **Table 7** (reprint from Yale Clinical Research Group) that used the Fontaine classification were adjusted in two ways: a) the average of the percentage of Rutherford 5 or 6 in the other studies as reported in b) the odds ratio. The adjusted numbers were very similar between the two methods so for this document, the odds ratio adjusted numbers will be used. After the odds ratio adjustments,

STATISTICAL ANALYSIS PLAN

the final AFS rate point estimate was 42.0% with an upper 95% confidence limit of 51.2%. However, in acknowledgement of FDAs concern around the performance goal and the previous discussions since 2017, LimFlow is not proposing to change the previously communicated performance goal based on the prior Yale work where the AFS rate point estimate was 43.7%, with an upper 95% confidence limit of 53.5%. Since the hypothesis test for this study is a test for superiority, the performance goal is set at the upper 95% confidence limit (UCL) of 53.5%, rounded up to 54%.

**Table 7: Reprint of from YCRG:

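### The Rutherford secondary endpoint is defined without a direction, so a worsening from class 5 to 6 meets it just as an improvement does

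*SAP*

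**What the plan says.** SAP 3.2 lists a change in Rutherford classification among the secondary objectives: "Defined as a change of one class or greater, as evaluated at 30 days, 3 and 6 months". Protocol synopsis and Protocol 4.8 use the same words. The SAP synopsis also has them, split by a page break ("class or greater, as evaluated at 30 days, 3 and 6 months").

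Eligibility limits entry to "Rutherford Classification 5, ischemic ulceration" or "Rutherford Classification 6, ischemic gangrene". The comparison table in SAP Appendix 1 ends at category 6, described as "Major tissue loss – extending transmetatarsally; functional foot no longer salvageable".

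SAP 7 plans descriptive summaries with 95% confidence intervals and no hypothesis tests. Binary endpoints "will be summarized as a proportion, with a 95% confidence interval computed via an exact binomial calculation". A second bullet begins "Secondary endpoints that involve the occurrence (or not) of events at times", sets the limit at 30 days or later, and says that these "will be summarized with Kaplan-Meier time-to-event methods". Neither bullet names the Rutherford endpoint.

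Two other provisions matter. Under Protocol 5.9, subjects leave the study at major amputation or death. Under Protocol 11.5.1, proportions are calculated on subjects whose value is known.

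**The concern.** A change can go either way. A subject who enters in class 5 and moves to class 6 has changed by one class and satisfies the definition as fully as one who moves to class 4. If the rule is programmed as written, deterioration raises the figure that a reader will take as a sign of benefit.

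The method is also open. A class recorded at a visit is a state that can reverse, and the two bullets of SAP 7 would treat it differently. Nor is there a rule for subjects who die or lose the limb before the visit. At stake is whether this secondary result can be interpreted; the decision on the performance goal does not depend on it.

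**Working it through.** The documents give no expected rate, power or sample size for this endpoint, so there is no stated figure to reproduce. The check sets the definitions side by side and then shows the effect with assumed counts.

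**1. Is a direction given anywhere?** None of the four statements contains one, and SAP 7 adds neither a direction, a shift table nor a separate count of worsening. The other clinical outcomes in the same lists do name the favourable result: patency as absence of occlusion, limb salvage as freedom from amputation, wounds as complete healing or reduced area.

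**2. Can worsening occur on the scale?** Yes, for class 5 entrants (5 to 6). It cannot for class 6 entrants, because 6 is the top category.

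**3. Size.** Let *i* be the proportion improved and *w* the proportion worsened. The endpoint as written reads *i* + *w*, so it exceeds the improvement rate by exactly *w*. With *i* = 40% assumed:

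| Worsened *w* (assumed) | Endpoint as written | Improved |
|---|---|---|
| 5% | 45% | 40% |
| 15% | 55% | 40% |
| 25% | 65% | 40% |

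Each row needs a class 5 share of at least *w*.

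**4. The same report from different results.** Take N = 105 (the SAP maximum) and 42 subjects with any change (assumed). The endpoint reads 42/105 = 40.0%, exact 95% CI 30.6 to 50.0, in every row:

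| Improved / worsened | Improvement only (exact 95% CI) |
|---|---|
| 42 / 0 | 40.0% (30.6 to 50.0) |
| 21 / 21 | 20.0% (12.8 to 28.9) |
| 0 / 42 | 0% (0 to 3.5) |

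**5. What the reported figure does imply.** If a share *s* enters in class 5 and a proportion *p* shows any change, at most *s* can have worsened. The proportion improved therefore lies between max(0, *p* − *s*) and *p*. The documents do not give *s*. At *p* = 0.50, *s* = 0.3 gives 0.20 to 0.50, while *s* = 0.5, 0.7 or 0.9 gives 0 to 0.50.

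**6. Method.** Suppose Kaplan-Meier were applied to the first change. A subject who goes 5, 6, 4 at the three visits has the event at 30 days because of a worsening. A subject who goes 5 to 4 at 30 days and is back at 5 by 6 months still counts at 6 months. A binomial proportion at each visit avoids both results, but it still needs a direction.

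**7. Denominator.** Subjects who die or have a major amputation exit and have no later class, so a proportion on known values leaves them out. Assume 42 improved among 105 enrolled and that every AFS failure lacks a 6-month class. Using AFS rates that appear in SAP 6.1 and 6.3:

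| AFS at 6 months | Assessable (105 × AFS) | Improved, known values only | Improved, all 105 |
|---|---|---|---|
| 0.54 | 57 | 42/57 = 74% | 40% |
| 0.70 | 74 | 42/74 = 57% | 40% |
| 0.75 | 79 | 42/79 = 53% | 40% |

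**The case against.** The best reply is that improvement is plainly meant and that little depends on it. The endpoint is descriptive, with no threshold or test. Rutherford class is recorded at baseline, 1, 3 and 6 months and later (Protocol Table 1), and individual listings are planned (SAP 9.4), so direction can be recovered. Serious deterioration also shows in AFS, limb salvage and wound healing. All of this stands, and it keeps the point minor. It does not close the gap, because a listing is not a planned summary and a direction chosen after the data are seen is not pre-specified.

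Four stronger readings are tempting, and the documents do not support them.

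- A reader might infer that the proportion can never show benefit. Class 6 entrants can only improve on the scale, so a figure above the class 5 share would imply some improvement, as a lower bound.
- A reader might infer that Kaplan-Meier is the planned analysis. It is a plausible reading of SAP 7, but the binary bullet fits as well.
- A reader might set the 55% against a net benefit of 40 − 15 = 25%. Neither document defines a net benefit. The relevant comparison is the 40% improved, a gap of 15 points.
- A reader might blame the missing direction for dependence on the class 5/6 mix at entry. An improvement-only proportion can also depend on that mix if improvement rates differ by baseline class.

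Scoring death and amputation as not improved is a separate choice, and the missing direction does not force it. It is recommended because of the exit and denominator rules in Protocol 5.9 and 11.5.1.

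**Conclusion.** The point holds as a defect in the definition of a descriptive secondary endpoint. The rule as written counts a 5-to-6 worsening as meeting the endpoint, and the reported proportion does not by itself identify improvement. The overstatement equals the proportion worsened: 15 points in the example of 40% improved and 15% worsened. Those rates are assumptions, and the possible overstatement is capped by the class 5 share at entry, which is not given. SAP 7 additionally leaves the method unclear. The primary test, its type I error and the sample size are unaffected.

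**What to change.** In all four places (Protocol synopsis and 4.8, SAP synopsis and 3.2), define the endpoint as improvement: a decrease of at least one class from baseline at 30 days, 3 months and 6 months.

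In SAP 7:

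- name the endpoint and assign it to exact binomial proportions at each visit;
- count death or major amputation before the visit as not improved, so that these subjects stay in the denominator;
- report worsening separately, with a shift table of baseline class by visit.

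The cost is a few sentences and one table. The class assessments are already scheduled, so no new data are needed. The reported proportion may be lower than under the present wording.

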#### 4.8 Secondary Endpoints

**Primary Patency:** Defined as absence of occlusion of the endovascular intervention that is maintained without the need for additional or secondary surgical or endovascular procedures, at 30 days and 6 months.

**Primary Assisted Patency:** Defined as absence of occlusion of the endovascular intervention that is maintained with the use of additional or secondary surgical or endovascular procedures, as long as occlusion of the primary treated site has not occurred, at 30 days and 6 months.

**Secondary Patency:** Defined as absence of occlusion of the endovascular intervention that is maintained with the use of additional or secondary surgical or endovascular procedures after occlusion occurs, at 30 days and 6 months.

**Limb Salvage:** Defined as percentage of subjects with freedom from above-ankle amputation of the index limb, evaluated at 30 days, 3 and 6 months.

**Change in Rutherford Classification:** Defined as a change of one class or greater, as evaluated at 30 days, 3 and 6 months.

**Technical Success:** Defined as the successful creation of an arteriovenous fistula in the desired limb location with immediate morphological success.

**Procedural Success:** Defined as the combination of technical success, and absence of all-cause death, above-ankle amputation or clinically driven major re-intervention of the stent graft at 30 days.

**Target Wound Healing:** Defined as complete healing of the patient's target wound as evaluated at 30 days, 3, 6, 9 months, and 1 year.

**All Wound Healing:** Defined as complete healing of the patient's wounds as evaluated at 30 days, 3, 6, 9 months, and 1 year.

**All Wound Area Reduction:** Defined as reduction in area of the patient's wounds as evaluated at 30 days, 3, 6, 9 months, and 1 year.

**Freedom from Contrast-Induced Nephropathy:** Defined as subjects without acute (within 72 hours after intravenous contrast administration) impairment of renal function, measured as an absolute  $\geq 0.5$  mg/dL (44  $\mu\text{mol/L}$ ) increase compared to baseline SCr value that results in a value above the upper limit of the normal range.

**Procedure Time:** Defined as the time of the first puncture (venous or arterial) to when the last catheter is removed.

**Radiation Exposure:** Defined as patient radiation exposure (in milligray) during the procedure.

**Contrast Volume:** Defined as the total volume of contrast media (in milliliters) given during the procedure.

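### SAP section 3.2, the list that SAP section 7 analyses, differs from Protocol 4.8 on Technical Success, All Wound Area Reduction and contrast-induced nephropathy

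*SAP*

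**What the plan says.** SAP section 7 does not list the secondary endpoints itself. It says "A listing of secondary endpoints is given in Section 3.2" and then gives methods by type: exact binomial intervals for binary endpoints, Kaplan-Meier for events at 30 days or later, and normal-theory intervals for continuous endpoints. The list in SAP 3.2 is therefore the one that section 7 puts into effect.

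**Technical Success.** SAP 3.2 requires "successful placement of the arterial and venous catheters in the desired location in the limb, ability to place the stent-grafts", and then "completion of the endovascular procedure, and immediate morphological success". Protocol 4.8 has "Defined as the successful creation of an arteriovenous fistula in the desired limb location with immediate morphological success", and the SAP synopsis (section 1) agrees with the protocol. In SAP 3.2, Procedural Success is "Defined as the combination of technical success" with the absence of three 30-day events; Protocol 4.8 builds it the same way.

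**All Wound Area Reduction.** Protocol 4.8 includes it: "Defined as reduction in area of the patient's wounds as evaluated at 30 days, 3, 6, 9 months, and 1 year". The SAP synopsis has an entry that begins "All Wound Area Reduction: Defined as reduction in area of the". SAP 3.2 has no such entry.

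**Contrast-induced nephropathy.** Protocol 4.8 counts a rise of at least 0.5 mg/dL as a case only if it is an "increase compared to baseline SCr value that results in a value above the upper limit of the normal range". The protocol synopsis and the protocol's definitions (section 15) carry the same condition. SAP sections 1 and 3.2 stop at the 0.5 mg/dL rise.

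**The concern.** A programmer who follows section 7 to section 3.2 would label Technical Success and Procedural Success by a rule that is not in the protocol. The same programmer would find one protocol endpoint missing from the working list, and would count nephropathy more broadly than the protocol does. For the first two items the SAP also disagrees with its own synopsis, so two readers of the same SAP could produce different tables. The SAP explains its change of maximum sample size in section 4 but gives no reason for these differences.

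The Per Protocol population may be touched as well. SAP 5.2 requires a successful procedure without saying which success definition applies.

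Technical Success is recorded at the procedure (Protocol 5.6), the trial is open and single-arm, and this SAP was revised after the N=90 assessment. The definition should therefore be settled on paper before the final tables are made.

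**Working it through.** The plan states no figure for this point, so there is none to reproduce. The check is a comparison of the texts, plus the arithmetic of one reclassified subject.

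**1. Count of endpoints.** Protocol 4.8 lists primary, primary assisted and secondary patency (3); limb salvage and Rutherford change (2); technical and procedural success (2); target wound healing, all wound healing and all wound area reduction (3); nephropathy (1); procedure time, radiation and contrast volume (3). The total is 3 + 2 + 2 + 3 + 1 + 3 = 14. SAP 3.2 has the same items without wound area reduction: 14 − 1 = 13.

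**2. Definitions side by side.**

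| Endpoint | Protocol 4.8 | SAP section 1 | SAP 3.2 |
|---|---|---|---|
| Technical Success | Fistula made at the intended site; immediate morphological success | As protocol | Both catheters positioned; stent-grafts placeable; procedure finished; immediate morphological success |
| All Wound Area Reduction | Listed, five time points | Listed | Absent |
| Nephropathy | Rise ≥ 0.5 mg/dL and result above upper limit of normal | Rise only | Rise only |

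**3. Technical Success: direction.** Morphological success is common to both definitions; the rest differs. The protocol rule needs a fistula and does not mention each stent-graft. A limb with a fistula, where one intended stent-graft could not be placed, can pass the protocol rule and fail SAP 3.2. SAP 3.2 never names a fistula, so on its words it could also pass a subject whom the protocol rule fails. Immediate morphological success has no entry in the protocol's definitions section to close that gap. Neither set contains the other.

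Let a be the number of subjects who meet only the protocol rule, b the number who meet only the SAP 3.2 rule, and N the number analysed. Then

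SAP rate − protocol rate = (b − a) / N.

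The documents give neither a nor b, so sign and size are both open. One subject is worth 1/105 = 0.0095, or 0.95 percentage points, at the SAP's maximum, and 1/60 = 0.0167, or 1.67 points, at the minimum. This assumes that every enrolled subject is in the denominator.

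**4. Procedural Success.** A subject who dies, has an above-ankle amputation or has a clinically driven major re-intervention of the stent-graft by 30 days fails under either definition. A discordant subject therefore moves Procedural Success by 1/N only if none of these occurred.

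**5. Nephropathy: direction.** Let A be a rise of at least 0.5 mg/dL and B a resulting value above the upper limit of normal. The protocol case is A and B together; the SAP case is A alone. Every protocol case is a SAP case, so

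freedom (SAP) = 1 − P(A) ≤ 1 − P(A and B) = freedom (protocol),

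and the gap is P(A and not B). With an upper limit u, a subject in the gap needs a baseline of at most u − 0.5 mg/dL. If u were 1.2 mg/dL (an assumption; the documents give no limit), that is a baseline of at most 1.2 − 0.5 = 0.7 mg/dL, and the ceiling moves one for one with u. The documents give no distribution of baseline creatinine, so the frequency cannot be computed.

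**The case against.** The strongest reply is that these are wording slips with little practical effect, and parts of it stand.

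- **Descriptive only.** Section 7 plans no hypothesis tests for secondary endpoints, so the primary amputation-free survival test, its type I error and its power are untouched. This stands, and it caps the importance of the point.
- **Technical Success may coincide in practice.** Protocol 5.5 and the notes to the assessment schedule treat stent-graft implantation as the working threshold, so most procedures may score the same under both rules. This is plausible. No passage shows that a discordant case is expected, but none makes the rules equal.
- **Nephropathy is adjudicated.** Protocol 7.2 has the Clinical Events Committee adjudicate contrast-induced nephropathy and says that adjudicated events feed the endpoint analysis. Protocol 4.10.5 has the committee trained on the protocol and its defined terms. The analysed events may already follow the protocol definition. In that case the SAP label would not match the data behind it, so the text still needs correcting.
- **Wound area is not gone from the SAP.** The synopsis keeps it, the continuous method in section 7 is generic with examples, the core laboratory analyses wound data, and listings of endpoints are planned. A reader might infer that the endpoint has been dropped or will have no estimate. The documents do not go that far: it is missing from the list that section 7 uses, and section 7 does not name it.

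**Conclusion.** The point holds. The SAP's operative list conflicts with the protocol in three places. On Technical Success and All Wound Area Reduction it also conflicts with the SAP's own synopsis. As written, this is an inconsistency to correct before the final analysis, with consequences confined to descriptive secondary reporting and possibly to membership of the Per Protocol population.

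What is firm is the value of one reclassified subject for Technical Success (0.95 points at N=105, 1.67 at N=60) and the direction for nephropathy (equal or lower freedom under the SAP wording). The number of subjects affected is unknown for both.

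Three stronger readings are not supported:

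- A reader might infer that SAP 3.2 is the stricter rule and will lower the Technical Success rate by several points. Neither definition contains the other, and the documents give no discordance rate.
- A reader might take the remark in Protocol 10.5 about stopping the device in favour of alternate devices as a route to a fistula that counts under one rule only. That line is a risk-control statement. It does not describe completing a fistula with another device, and SAP 3.2 does not address a non-study graft.
- A reader might infer from the timing of the SAP revision that definitions were chosen after results were seen. Two definitions in one SAP leave that possible, but nothing in the documents suggests it happened. It is also conjecture that the core laboratory scores one rule under the other's label, because its manual is not among the documents.

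**What to change.** Before the final analysis:

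1. Replace the Technical Success text in SAP 3.2 with the Protocol 4.8 definition, and confirm that the core laboratory scores that definition. State in SAP 5.2 which success definition the Per Protocol population uses.
2. Add All Wound Area Reduction to SAP 3.2 at the protocol's five time points (30 days, 3, 6 and 9 months, 1 year), and name it among the continuous endpoints in section 7.
3. Restore the upper-limit-of-normal condition in SAP sections 1 and 3.2, or record why it was dropped, and confirm that the wording matches what the Clinical Events Committee adjudicates.

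The cost is SAP wording and one table from wound measurements that the core laboratory already receives (Protocol 4.10.3). A stated secondary rate may change slightly.
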